DBTP	double-blind treatment period
DSM-5	Diagnostic and Statistical Manual of Mental Disorders, Fifth Edition
DxV	Diagnostic Validation
ECG	electrocardiogram, electrocardiographic
eCRF	electronic case report form
ET	early termination
ICF	informed consent form
IP	investigational product
LLN	lower limit of normal
MADRS	Montgomery-Åsberg Depression Rating Scale
MDD	major depressive disorder
MedDRA	Medical Dictionary for Regulatory Activities
mITT	modified intent to treat

MMRM	mixed-effects model for repeated measures
PCS	potentially clinically significant
PID	patient identification
PK	pharmacokinetic
QTc	QT interval corrected for heart rate
QTcB	QT interval corrected for heart rate using the Bazett formula ($QTcB = QT/(RR)^{1/2}$)
QTcF	QT interval corrected for heart rate using the Fridericia formula ($QTcF = QT/(RR)^{2/3}$)
SAE	serious adverse event
SAP	statistical analysis plan
SE	Standard Error
SFUP	Safety Follow-up Period
SI	Le Système International d'Unités (International System of Units)
TEAE	treatment-emergent adverse event
UDS	urine drug screen
ULN	upper limit of normal

3.0

HISTORY OF CHANGE

Section No.	Section Name	Description
General Notes		
The following changes are implemented in the statistical sections of protocol amendment 1 (dated May 22, 2019):
 
1. The gatekeeping serial testing procedure was replaced by the graphical testing procedure to adjust for multiple comparisons in the primary and secondary efficacy parameters for both rapastinel doses versus placebo. The section of “interim analysis” was added based on the proposal agreed by the FDA (response dated dd May 2019).2. The section of “determination of sample size” was revised to reflect the associated changes in the significance level and associated power for the final primary efficacy analyses due to the addition of interim analysis. 
These changes are now implemented in Sections 10.2 (KEY SECONDARY EFFICACY PARAMETERS), 13.0 (INTERIM ANALYSIS) and 14.0 (DETERMINATION OF SAMPLE SIZE) of this SAP amendment.
 
In addition, other revisions were documented in this history of change and implemented in this SAP amendment.

10.2	KEY SECONDARY EFFICACY PARAMETERS	The gatekeeping testing procedure was replaced by the graphical testing procedure to adjust for multiple comparisons in the primary and secondary efficacy parameters for both rapastinel doses versus placebo.
11.3	VITAL SIGNS	The orthostatic hypotension was specified to be summarized for pre-dose, post-dose and other visits without IP administration separately for the DBTP.
13.0	INTERIM ANALYSIS	The blinded sample-size re-estimation was replaced by an unblinded interim analysis in order to identify early signs of futility.
14.0	DETERMINATION OF SAMPLE SIZE	The sample size estimation was revised to reflect a reduced significance level (from 0.05% to 0.049%) and associated power for the final primary efficacy analyses due to the addition of interim analysis.

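### Does the exponent 2/3 printed for QTcF in the SAP's abbreviation list put a wrong heart-rate correction into the analysis?

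*SAP*

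**What the plan says.** QTcF is defined in one place in the public SAP text, the list of abbreviations: "QT interval corrected for heart rate using the Fridericia formula ($QTcF = QT/(RR)^{2/3". The entry directly above defines the Bazett version: "QT interval corrected for heart rate using the Bazett formula ($QTcB = QT/(RR)^{1/2". The closing bracket after each exponent is left out of these quotations; the exponents are 2/3 and 1/2. The unit of RR is not given.

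No other visible section restates either formula. The public text of the safety chapter contains Section 11.1 (adverse events) and then continues with Section 13.0 (interim analysis). The history of change mentions a Section 11.3 on vital signs, so the plan has safety sections that are not visible here. Section 16.3 refers to the determination of potentially clinically significant values, but no ECG criteria for these appear in the public text. Section 4.0 places the specifications of tables, figures and listings in a separate document.

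**The concern.** The Fridericia correction is by definition the cube root: QT/RR^(1/3). An exponent of 2/3 belongs to a different and much stronger correction. The Bazett line above makes the mismatch stand out. Fridericia should correct less strongly than Bazett (1/3 < 1/2), but the two printed exponents make it correct more strongly (2/3 > 1/2).

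If a programmer took the formula literally, every QTcF value at a heart rate other than 60 bpm would be wrong. The error would not be random. It would inflate QTcF at faster heart rates and deflate it at slower ones, and so distort summaries and any count of patients above a QTcF limit. A SAP is meant to fix technical detail, and an explicit formula in it should agree with its name, so the entry deserves a check.

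**Working it through.** **Inputs.** The exponents 2/3 (QTcF) and 1/2 (QTcB) come from the SAP's list of abbreviations. The exponent 1/3 is the definition of the formula that the SAP names. Three things are assumed because the SAP does not give them: RR in seconds (RR = 60/HR), the heart rates below, and an uncorrected QT of 400 ms.

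**Formulas.** The ratios do not depend on QT.

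- Printed QTcF / cube-root QTcF = RR^(1/3 − 2/3) = (HR/60)^(1/3)
- Printed QTcF / QTcB = RR^(1/2 − 2/3) = (HR/60)^(1/6)
- Cube-root QTcF / QTcB = RR^(1/2 − 1/3) = (HR/60)^(−1/6)

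**Ratios.**

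| HR (bpm) | RR (s) | Printed / cube root | Printed / QTcB | Cube root / QTcB |
|---|---|---|---|---|
| 50 | 1.2 | 0.941 | 0.970 | 1.031 |
| 60 | 1.0 | 1 | 1 | 1 |
| 75 | 0.8 | 1.077 | 1.038 | 0.963 |
| 100 | 0.6 | 1.186 | 1.089 | 0.918 |

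**In milliseconds, for an assumed QT of 400 ms.**

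| HR (bpm) | QTcB | Printed QTcF | Cube-root QTcF | Printed minus cube root |
|---|---|---|---|---|
| 50 | 365.1 | 354.2 | 376.4 | −22.2 |
| 60 | 400.0 | 400.0 | 400.0 | 0.0 |
| 75 | 447.2 | 464.2 | 430.9 | +33.3 |
| 100 | 516.4 | 562.3 | 474.3 | +88.0 |

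The printed exponent is therefore not a harmless variant of the named formula: the two agree only at 60 bpm.

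**Does anything use the printed form?** The arithmetic matters only if an analysis takes its formula from this line.

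1. No visible section computes QTcF, sets a limit on it or refers back to the abbreviation list for a derivation.
2. The ECG section and the criteria for clinically significant ECG values, where a derivation would normally be stated, are not in the public text. What they say cannot be held against the plan.
3. The entry gives the method by name as well as by symbol. A programmer or ECG vendor asked for Fridericia would apply the cube root.
4. The primary and key secondary analyses (Sections 10.1 and 10.2), the split of the Type I error (Section 13.0) and the sample size (Section 14.0) concern the MADRS total score and contain no ECG quantity.

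**Is the digit certain?** The text was extracted from a PDF, and the formula appears in re-encoded mathematical notation. The whole discrepancy is a 2 in place of a 1 in a small superscript. The Bazett exponent next to it was read correctly, so a misreading is possible but not shown.

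**The case for a change.** The best case for asking for a change is this. In the visible text the glossary line is the only definition of QTcF, and it is wrong as read. The expression is complete and well formed, and its neighbour was read without error, so an extraction fault should not simply be presumed. The correction would cost one character. The error, if it were carried into a program, would be large: about 33 ms at 75 bpm for a QT of 400 ms. It would also be easy to detect. With the cube root, QTcF lies below QTcB in every record above 60 bpm and above it in every record below 60 bpm; the printed form reverses that order.

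The mismatch between name and exponent stands, and so does the arithmetic. What does not stand is the step from a glossary entry to a wrongly fixed analysis. That step needs someone to program an unfamiliar exponent under a well-known name, and it needs the unseen ECG section to be silent or wrong as well. The document supports neither. The millisecond figures describe that hypothetical case, at assumed heart rates and an assumed QT, and are not evidence that results would be affected.

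**Conclusion.** The entry as read is wrong, but it is a clerical matter and calls for no change to the planned analysis. The intended method is clear from its name, no visible analysis depends on the printed exponent, and the digit itself may come from the PDF conversion. The effect shown on results is nil. The conditional effect, if QTcF were programmed as printed with RR in seconds, is a factor of (HR/60)^(1/3): +7.7% at 75 bpm and −5.9% at 50 bpm.

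This conclusion assumes that analysts and ECG vendors follow the named method, and that the safety sections absent from the public text do not adopt the exponent 2/3. If such a section were found to derive QTcF with 2/3, the point would become a real error in a safety analysis, though still one without bearing on the efficacy conclusions.

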4.0 INTRODUCTION

[figure not shown]
This statistical analysis plan (SAP) provides a more technical and detailed elaboration of the statistical analyses of the efficacy and safety data as outlined in the Study RAP-MD-32 protocol amendment 1 (dated May 22, 2019). Specifications of tables, figures, and data listings are contained in a separate document. The SAP for pharmacokinetic, pharmacodynamic and/or health economics and outcomes research data (if applicable) will be prepared separately.

Study RAP-MD-32 is a Phase 3, multicenter, randomized, double-blind, placebo-controlled, parallel-group study in patients 18 to 75 years of age who meet the Diagnostic and Statistical Manual of Mental Disorders, Fifth Edition (DSM-5) criteria for major depressive disorder (MDD). The symptoms and severity of MDD will be assessed based on their Montgomery-Åsberg Depression Rating Scale (MADRS) and Clinical [REDACTED]. All patients will be treatment naive (defined as those who have not received antidepressant, or have received antidepressant but not meeting adequate dose or duration criteria per the Antidepressant Treatment Response Questionnaire [ATRQ]) in the present episode or inadequate response (<50% reduction in depressive symptoms) to 1 to 3 antidepressant therapies (ADTs) given at adequate doses for ≥ 4 weeks during the present episode.

The study will include a total of 10 visits and will be approximately 10 weeks in duration:

- Up to 2-week screening period
- 6-week double-blind treatment period
- 2-week safety follow-up period (no treatment) for patients who do not roll over into the extension study

Signed informed consent from the patient or the patient's legally authorized representative will be obtained before any study-related procedures are begun. Patients will wash out any previous ADT and/or prohibited medications during the screening period. Patients meeting the eligibility criteria at the end of Visit 2 will be randomized in a ratio of 1:1:1 to one of the three treatment arms: rapastinel 900 mg IV weekly, rapastinel 450 mg IV weekly, or placebo IV weekly. The double-blind treatment period (DBTP) starts with the first dose of study treatment. Upon completion of the DBTP, patients may be eligible to enter the extension study. Patients who do not enter the extension study will enter a 2-week safety follow-up period. Efficacy and safety assessments will be conducted at the clinic 1 day following the treatment day in the 1st week and at the ends of weeks 1, 2, 3, 4, 5 and 6 of the DBTP. Patients prematurely discontinuing from the study, regardless of cause, will be seen for a final evaluation. The schedule of evaluations for Study RAP-MD-32 is presented in [Table 4-1](#).

[figure not shown]

[figure not shown]
5.0 OBJECTIVES

The objectives of this study are to evaluate the efficacy, safety, and tolerability of rapastinel as monotherapy treatment in patients with MDD.

Efficacy Objectives

- **Primary efficacy objective:** To evaluate the efficacy of rapastinel (450 mg IV) versus placebo and rapastinel (900 mg IV) versus placebo in the treatment of MDD, as measured by the change from baseline Montgomery-Åsberg Depression Rating Scale (MADRS) total score at end of treatment (end of Week 6)
- **Key secondary efficacy objective:** To evaluate the efficacy of rapastinel (450 mg IV) versus placebo and rapastinel (900 mg IV) versus placebo in the treatment of MDD, as measured by the change from baseline MADRS total score at 1 day post-first dose of treatment

6.0 PATIENT POPULATIONS

The following populations will be considered in the statistical analysis of the study.

6.1 SAFETY POPULATION

The Safety Population will consist of all randomized patients who received at least 1 dose of randomized IP.

6.2 MODIFIED INTENT-TO-TREAT POPULATION

The Modified Intent-to-Treat (mITT) Population will consist of all patients in the Safety Population who had at least 1 post-baseline assessment of the MADRS total score.

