10.0 EFFICACY ANALYSES

All efficacy analyses will be based on the mITT Population, unless stated otherwise. The baseline for each specific efficacy endpoint is defined as the last non-missing measurement prior to the first dose of randomized IP. All statistical hypothesis tests will be performed at the 2-sided significance level of 5% for main effects. All confidence intervals (CIs) will be 2-sided 95% CIs, unless stated otherwise.

For efficacy analyses in which pooled study center is a factor, a small center will be defined as a center with < 2 patients in ≥ 1 treatment group in the mITT Population. Small centers will be pooled to form pseudo-centers so that each treatment group includes ≥ 2 mITT patients within the center. Pooling will be done using the following algorithm:

Based on the number of mITT patients, small centers will be ordered from the largest to the smallest, and centers of the same size will be ordered from the largest center code to the smallest center code. The pooling process starts with the largest small center from the top, which will be pooled with the smallest from the bottom until a non-small center is formed. The process will be repeated using the small centers left out after the first pass. If any centers are left out at the end of the process, they will be pooled with the smallest pseudo-center. If there is > 1 smallest pseudo-center, the pseudo-center with the smallest center code will be selected. In case the pseudo-center formed by pooling all small centers is still a small center, it will be pooled with the smallest non-small center. If there is > 1 smallest non-small center, the one with the smallest center code will be selected.

The efficacy analyses using the mITT population will be performed based on the treatment to which the patient is randomized regardless of the actual treatment received.

The efficacy analyses of MADRS assessments will be based on the rater-administered MADRS.

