10.1 PRIMARY EFFICACY PARAMETER

The primary efficacy parameter will be the change from baseline in MADRS total score at the end of treatment (end of Week 6). The MADRS contains 10 items that assess depression, with scores for each item ranging from 0 (absence of symptoms) to 6 (symptoms of maximum severity). The MADRS total score is the sum of the 10 individual items. If more than 2 items are missing, the total score will be set to missing. If there are multiple assessments of MADRS total score for the same day visit of a patient, only the last assessment will be used in the analysis.

The primary parameter will be analyzed using a mixed model for repeated measures (MMRM) with terms for treatment, pooled study center, visit (Day 1 visit and the weekly visits from Week 1 to Week 6), baseline, and treatment-by-visit and baseline-by-visit interactions. An unstructured covariance matrix will be used to model the covariance of within-patient scores. The Kenward-Roger approximation will be used to estimate denominator degrees of freedom (Kenward et al, 1997). This analysis will only use the observed postbaseline scores without imputation of missing values. The treatment differences for rapastinel 450 mg versus placebo and rapastinel 900 mg versus placebo will be estimated and reported along with the corresponding 95% CIs and p-values.

In the case that the MMRM model with unstructured covariance fails to converge with the default algorithm, then the Fisher scoring algorithm will be used to provide better initial values of the covariance parameters; if the model still does not converge, a simplified model without the factor of the pooled study center will be used to find the initial values of the covariance parameters. In the rare event that model still does not converge after using those initial values, simplified covariance structures will be used to fit the model in the following order until the model converges: (1) ante-dependence, (2) heterogeneous autoregressive, (3) Toeplitz, and (4) compound symmetry.

To assess the robustness of the primary MMRM results to the possible violation of the missing-at-random assumption, a sensitivity analysis will be conducted.

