The sensitivity analysis will use a pattern-mixture model based on non-future dependent missing value restrictions (Kenward et al, 2003). The pattern for the pattern-mixture model will be defined by the patient's last visit with observed value. The observed MADRS total score at a visit is assumed to have a linear relationship with the patient's prior measurements. The missing values will be imputed under the assumption that the distribution of the missing observations differs from the observed only by a shift parameter value Δ . The dataset with observed and imputed values will be analyzed using the same model as the primary analysis for between-treatment group comparisons at the end of the treatment. The imputation of missing values and the analysis will be performed 20 times and the inference of this sensitivity analysis will be based on the combined estimates using the standard multiple imputation technique. The values of Δ will be selected as 0 to 8.

[figure not shown]

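### The missing-at-random sensitivity analysis runs on the mITT set, so dosed patients with no post-baseline MADRS are never shifted by Δ (small gap, cheap to close)

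*SAP*

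**What the plan says.** Four statements in the SAP combine.

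- Section 6.1 sets the Safety Population as "all randomized patients who received at least 1 dose of randomized IP". Section 6.2 narrows this for mITT to "all patients in the Safety Population who had at least 1 post-baseline assessment of the MADRS total score".
- Section 10.0 sets the default: "All efficacy analyses will be based on the mITT Population, unless stated otherwise".
- Section 10.1 gives the purpose of the extra analysis: "To assess the robustness of the primary MMRM results to the possible violation of the missing-at-random assumption, a sensitivity analysis will be conducted".
- Section 10.1 then describes the method. "The pattern for the pattern-mixture model will be defined by the patient's last visit with observed value". Missing scores are imputed with a shift Δ, whose values "will be selected as 0 to 8". "The dataset with observed and imputed values will be analyzed using the same model as the primary analysis".

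The visible text of Section 10.1 names no analysis set for this step, so the Section 10.0 default applies.

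Three other places bear on how many patients are affected. Sections 4.0 and 10.1 plan a Day 1 assessment. Section 4.0 also says that anyone leaving early, for whatever reason, is to have a final evaluation. Section 7.0 reports mITT and Safety counts by treatment group.

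**The concern.** In the primary MMRM, a patient with a baseline score and nothing afterwards adds nothing to the likelihood. Leaving that patient out costs nothing there, and amounts to assuming missing-at-random given baseline.

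The sensitivity analysis exists to relax that assumption. Patterns are defined by the last visit with an observed score and mITT requires a post-baseline score, so a baseline-only pattern cannot occur. These patients keep the assumption at every Δ. The selection also rests on something that happens after the first infusion, so randomization does not protect it. Section 9.1 collects infusion interruptions and perceptual disturbances, so the SAP itself allows for events on the dosing day that might lead someone to leave.

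At stake is how the Δ results are read, in particular the Δ at which significance is lost. If baseline-only loss were more frequent on a rapastinel dose, that point would look a little more robust than it is.

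**Working it through.** **Inputs from the SAP.** Section 14.0: 230 patients per group, SD 10, within-patient correlation 0.6, dropout 20%, difference 3.5 points, two-sided level 4.9%. Section 10.2: each dose is first tested at 0.0245. Section 10.1: Δ up to 8.

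**Input not in the SAP.** The share of dosed patients without a post-baseline MADRS is not given. I assume 1% to 5% per arm.

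**The plan's own figure.** Completers per arm = 230 × 0.8 = 184. SE = 10 × √(2/184) = 1.043. Power at 3.5 points and level 0.049 is 91.75%, against the stated 91%. The figure reproduces, and this point does not depend on it.

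**Shift in the Week 6 difference.** Let p be the share of an arm that is baseline-only, and d the amount by which those patients are worse at Week 6 than missing-at-random predicts. Then

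shift = p(active) × d(active) − p(placebo) × d(placebo).

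With a common d this is [p(active) − p(placebo)] × d.

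**Value of d when Δ = 8.**

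- The full shift persists to Week 6: d = 8.
- The shift enters at Day 1 and passes through the later regressions. If the 0.6 correlation is compound-symmetric and includes baseline, the Week 6 coefficient on Day 1 given baseline is 0.6/(1 + 0.6) = 0.375, so d = 3.
- The same, with a coefficient of 0.6: d = 4.8.

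| Assumed loss, active / placebo | d | Shift (points) | In SE (÷ 1.043) |
|---|---|---|---|
| 4% / 1% | 8 | 0.03 × 8 = 0.24 | 0.23 |
| 4% / 1% | 4.8 | 0.03 × 4.8 = 0.14 | 0.14 |
| 4% / 1% | 3 | 0.03 × 3 = 0.09 | 0.09 |
| 2% / 1% | 8 | 0.01 × 8 = 0.08 | 0.08 |
| 2% / 1% | 4.8 | 0.01 × 4.8 = 0.05 | 0.05 |
| 2% / 1% | 3 | 0.01 × 3 = 0.03 | 0.03 |
| equal | any common d | 0 | 0 |

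The largest entry is 0.24/3.5 = 7% of the planned difference.

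**Loss in one active arm only, d = 8.** Two of 230 patients (0.9%) take 3.5 to 3.43, five (2.2%) to 3.33, and twelve (5.2%) to 3.08.

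**How much loss would overturn a 3.5-point result.** A repeated-measures calculation (seven visits, compound symmetry 0.6, linear dropout to 20%) gives an SE of about 0.99 and a critical difference of about 2.23 at level 0.0245. The share needed in one arm is (3.5 − 2.23)/8 = 16%, or about 37 of 230 patients.

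**How much matters near the boundary.** The critical z at 0.0245 is 2.25. Adding 0.23 gives 2.48, or p of about 0.013. So a 0.23 SE shift changes the conclusion only for a result with p between about 0.013 and 0.0245.

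**The case against.** The case on the other side is strong on size.

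- **The group may be very small.** Section 6.2 asks for any post-baseline MADRS, not a Day 1 score. If the final evaluation in Section 4.0 includes a MADRS, the windows in Section 16.2 place a score from Day 2 to Day 10 (no Day 7 dose) at Day 7. The patient is then in mITT, and later missing visits are shifted. Whether that evaluation includes a MADRS cannot be seen, because the schedule table is not shown.
- **The loss is already visible.** Section 7.0 gives mITT and Safety counts by arm, and discontinuation reasons by arm for all randomized patients. A reader can apply the formula above.
- **Most missingness is stressed.** Every mITT patient who drops out after a first post-baseline score is shifted. On 20% dropout in one arm, a full shift moves the difference by 0.2 × 8 = 1.6 points.
- **No sentence in the SAP is wrong.** The mITT definition is explicit and consistently applied.

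Nearly all of this stands, with two limits. A table of counts is not an efficacy analysis and does not show where significance is lost. And the 1.6 points assumes the shift in one arm only, which Section 10.1 does not say. With Δ in all arms, equal dropout cancels, and a 3-percentage-point imbalance counts about the same in either group if the shift persists equally.

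A reader might go further and infer that the sensitivity analysis leaves missing-at-random untested, or that the exclusion favours rapastinel. The SAP supports neither. The first fails because later dropout is shifted. The second needs more loss, or worse outcomes among those lost, on the active arm; with equal loss and a common shift the effect is zero, and with more loss on placebo it works against the drug.

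**Conclusion.** The gap is real on the text: in the only visible analysis meant to relax missing-at-random, dosed patients without a post-baseline MADRS stay under that assumption at every Δ. It is a low-severity robustness point and does not show an error in the primary MMRM.

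Under an assumed loss of 4% versus 1%, the effect on the Week 6 difference is at most 0.24 points (0.23 SE) with the full 8 points persisting, and about 0.09 to 0.14 points with the shift entering at Day 1. These figures rest on the assumed loss rates, on a compound-symmetric correlation of 0.6 for the lower end, and on a Week 6 deviation no larger than Δ. A program that added a fresh shift at each missing visit could exceed the last of these. The SAP gives no count of such patients and no sign of imbalance between arms, so the actual effect may be nil.

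**What to change.** In Section 10.1, state that the pattern-mixture sensitivity analysis includes all Safety Population patients with a baseline MADRS, analysed as randomized. Add a baseline-only pattern. Its Day 1 score is imputed from the observed-data regression of Day 1 on baseline, shifted by Δ, and its later visits are imputed by the same sequential procedure as for the other patterns. The wording should make clear that Δ is added to the regression prediction, not to the baseline score, and that no value is simply carried forward. Keep mITT for the primary MMRM.

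The cost is a sentence or two in the SAP and one more pattern in the imputation program, with no new data. The sensitivity set will differ from the primary set by a few patients, and the Δ results may be slightly less favourable. The change should be made before unblinding so that it is credible.
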